DSMB	Data Safety Monitoring Board
EU	European Union
EudraCT	European drug regulatory affairs Clinical Trials
GCP	Good Clinical Practice
GDPR	General Data Protection Regulation; in Dutch: Algemene Verordening Gegevensbescherming (AVG)
IB	Investigator's Brochure
IC	Informed Consent
IMP	Investigational Medicinal Product
IMPD	Investigational Medicinal Product Dossier
METC	Medical research ethics committee (MREC); in Dutch: medisch-ethische toetsingscommissie (METC)
(S)AE	(Serious) Adverse Event
SPC	Summary of Product Characteristics; in Dutch: officiële productinformatie IB1-tekst
Sponsor	The sponsor is the party that commissions the organisation or performance of the research, for example a pharmaceutical company, academic hospital, scientific organisation or investigator. A party that provides funding for a study but does not commission it is not regarded as the sponsor, but referred to as a subsidising party.
SUSAR	Suspected Unexpected Serious Adverse Reaction

- UAVG** Dutch Act on Implementation of the General Data Protection Regulation; in Dutch: Uitvoeringswet AVG
- WMO** Medical Research Involving Human Subjects Act; in Dutch: Wet Medisch-wetenschappelijk Onderzoek met Mensen

SUMMARY

Rationale: Gastrointestinal malignancies are rare in children and adolescents. Consequently, data on clinical features, treatments and outcomes of these patients are limited.

Objective: We aim to describe the patient and tumor characteristics, treatments, and outcomes of children and adolescents diagnosed with primary gastrointestinal malignancies, and to analyze these data for trends over time. In addition, we want to explore independent prognostic factors for overall survival. Finally, we want to describe subsequent primary malignancies diagnosed among patients from the study cohort, as well as to calculate their risk of developing a second primary cancer relative to the general population. Data on children (aged 0-17 years at diagnosis) and young people aged 18-24 years at diagnosis are analyzed separately. Special focus is laid on patients with primary carcinomas of the gastrointestinal tract; particularly colorectal carcinoma.

Study design: This is an observational population-based cohort study based on the publicly available Surveillance, Epidemiology, and End Results (SEER) database.

Study population: Children (aged 0-17 years) and young people aged 18-24 years with a diagnosis of a primary gastrointestinal malignancy registered as their first primary malignancy in the SEER 17 database between 2000 and 2019.

Intervention: Not applicable.

Main study parameters/endpoints: Descriptive statistics of patient and tumor characteristics at diagnosis, first course treatments, overall survival, and subsequent primary malignancies.

Secondary study parameters/endpoints: 1) Time trends in incidence, stage at diagnosis, first course treatments, mortality, and overall survival. 2) Associations between the variables age at diagnosis, sex, race and origin, year of diagnosis, stage at diagnosis, and histologic category (when relevant) with overall survival in multivariable analysis. 3) Standardized incidence of second primary malignancies in patients who survived (i) two or more months, or (ii) five or more years after initial gastrointestinal cancer diagnosis, relative to the general population.

Nature and extent of the burden and risks associated with participation, benefit and group relatedness: No burden and/or risks; no benefit.

1. INTRODUCTION AND RATIONALE

Gastrointestinal (GI) malignancies – also called “digestive cancers” – are rare in children and adolescents¹. These malignancies develop in the GI tract and/or accessory digestive organs, including the liver, biliary tract and pancreas^{2,3}. Notably, the mouth, pharynx and salivary glands are also part of the GI system, but malignancies in these locations are generally classified within the group of head and neck cancers^{3,4}. Therefore, like in prior studies of digestive cancers², these malignancies are not investigated in this study; the term “GI tract” is used to refer to the alimentary canal running from the esophagus to the anus. Because of the rarity of GI malignancies in children and adolescents, data on clinical features, treatments and outcomes of these patients are limited.

Childhood is defined as the developmental period between 0 and 17 years of age⁵. Importantly, much debate still exists about the definition of adolescence^{5,6}. The United Nations (UN) and World Health Organization define adolescence as the period between 10 and 19 years of age. However, this definition dates back to the mid-20th century, with significant changes in human biological and social development since that time⁵. Therefore, Sawyer *et al.* recently proposed an expanded definition of adolescence, which encompasses the period between 10 and 24 years of age⁵. This new definition overlaps with those of the terms youth (defined by the UN as people aged 15-24 years) and young people (defined as people aged 10-24 years)^{5,6}. Adolescents have often been overlooked in health care, research and policy⁷; one growing response is that from pediatricians to more embrace adolescent health⁸. A recent survey among pediatricians in high-income North America revealed a mean preferred upper age limit of pediatric practice of 21.7 years, which was significantly higher than the mean current upper age limit of the pediatricians’ practices of 19.2 years⁸. To comply with this increasing focus of pediatricians on adolescent health, our study will include patients aged 0-24 years at primary gastrointestinal cancer diagnosis. Yet, the upper age limit of pediatric care is still below 18 years in many – particularly lower-income – countries⁸. Therefore, data on children (aged 0-17 years) and young people aged 18-24 years will be (preferably) analyzed separately – to ensure that the study results are appropriate to readers from different health care settings.

One common site of GI malignancies in children and adolescents is the liver. There are different types of primary liver cancer. The most common types in children are hepatoblastoma (HB), hepatocellular carcinoma (HCC) and undifferentiated embryonal sarcoma of the liver (UESL)⁹. Several (population-based) cohort studies investigating children and/or adolescents with hepatic malignancies have already been published^{10–13}. However, a comprehensive overview of population-based data on the different hepatic malignancies and other gastrointestinal cancers in children and adolescents is still lacking. Regarding malignancies with the GI tract as their primary site, lymphoma is one of the most common subtypes in children – often representing intestinal Burkitt lymphoma (BL)¹. Although the true primary site of hematologic malignancies is the hematopoietic system, we deliberately do not exclude these malignancies, because we want to investigate all cancers with the GI system as their primary location. Several (population-based) cohort studies investigating children and/or adolescents with BL have been published^{1,14}; however, these did not specifically focus on patients with gastrointestinal BL. Finally, limited data is currently available on children and adolescents with primary carcinomas of the GI tract, which predominantly include colorectal carcinoma (CRC) and gastric carcinoma (GC)^{15–18}. To address this limited data, our study will focus on patients with these rare cancers.

Lastly, recent studies have identified genetic predisposition in a significant proportion of children and adolescents with cancer, including young people with colorectal cancer^{19,20}. This partly explains the increased risk of subsequent malignant neoplasms among childhood cancer survivors²¹. In addition, specific treatments can also increase the risk of second primary malignancies (SPM)²². Many prior studies have investigated SPM in five-year childhood and/or adolescent cancer survivors^{22–27}. These studies exclude second cancers diagnosed within five years of initial cancer diagnosis; thereby, they reduce surveillance bias. However, recent population-based studies investigating SPM in children with cancer that survived two or more months revealed that a significant proportion of second cancers actually develop within those first five years after initial cancer diagnosis^{28–30}. In this study, the standardized incidence of SPM is therefore investigated in both groups: (i) patients that survived two or more months, and (ii) patients that survived five or more years after initial gastrointestinal cancer diagnosis.

2. OBJECTIVES

Primary Objective: To describe the patient and tumor characteristics, first course treatments, survival and subsequent primary malignancies of children and adolescents diagnosed with primary gastrointestinal malignancies.

Secondary Objective(s): 1) To investigate time trends in incidence, stage at diagnosis, first course treatments, mortality, and overall survival. 2) To explore independent prognostic factors for overall survival. 3) To calculate the standardized incidence of second primary malignancies in childhood and adolescent gastrointestinal cancer survivors, relative to the general population.

3. STUDY DESIGN

This is an observational population-based cohort study based on publicly available data of the Surveillance, Epidemiology, and End Results (SEER) database. The SEER Program collects cancer incidence and survival data from multiple population-based cancer registries in the United States of America (U.S.). SEER began collecting data in 1973 with a limited number of registries. Since 1973, the SEER Program has been expanded to cover numerous additional areas. SEER 17 is the largest registry grouping with complete data, and includes cancer cases registered from 2000 onwards in 17 cancer registries covering approximately 26.5% of the U.S. population (<https://seer.cancer.gov/registries/data.html>). Importantly, SEER recommends that when performing an analysis, researchers subset based on year or registry so that they have consistent geographic coverage for the period of the analysis. Accordingly, SEER does not provide datasets with varying registries and years of data (e.g. 1975-2000 data from SEER 8 registries and 2000-2019 data from SEER 17 registries). SEER 17 incidence data is used for this study, because the SEER 17 database contains the most cancer cases to investigate, when compared to SEER 12 (1992-2019) or SEER 8 (1975-2019) (<https://seer.cancer.gov/data-software/documentation/seerstat/nov2021/>).

The SEER Program registries routinely collect data on patient demographics, primary tumor site, tumor morphology, stage at diagnosis, first course of treatment, and follow-up for vital status. The mortality data reported by SEER are provided by the National Center for Health Statistics (NCHS). Notably, NCHS granted SEER permission to make available mortality data of the total U.S. population – based on death certificates – for the period 1969-2019. The population data used in calculating cancer rates is obtained from the Census Bureau.

4. STUDY POPULATION

4.1 Population (base)

All cases registered in the SEER 17 database between (and including) 2000 and 2019 (last data year in the April 2022 SEER data release).

4.2 Inclusion criteria

In order to be eligible for this study, a case must meet all of the following criteria:

- Age (at primary gastrointestinal cancer diagnosis) <25 years
- Diagnosis of a primary gastrointestinal malignancy as an individual's first primary malignancy, based on:
 - Primary site "digestive organs" (ICD-O-3 topography codes C015-C026)
 - Behavior code "malignant" (ICD-O-3 behavior code 3)

Selection of only those cases with a primary gastrointestinal malignancy as their first primary malignancy is done by setting the Multiple Primary Selection option on the Selection tab of SEER*Stat software to First Malignant Primary Only (Non-reported Assumed Malignant).

4.3 Exclusion criteria

None

4.4 Sample size calculation

Not applicable, given that the primary objective of this study is of descriptive nature.

5. TREATMENT OF SUBJECTS

Not applicable

5.1 Investigational product/treatment

Not applicable

5.2 Use of co-intervention (if applicable)

Not applicable

5.3 Escape medication (if applicable)

Not applicable

6. INVESTIGATIONAL PRODUCT

Not applicable

6.1 Name and description of investigational product(s)

Not applicable

6.2 Summary of findings from non-clinical studies

Not applicable

6.3 Summary of findings from clinical studies

Not applicable

6.4 Summary of known and potential risks and benefits

Not applicable

6.5 Description and justification of route of administration and dosage

Not applicable

6.6 Dosages, dosage modifications and method of administration

Not applicable

6.7 Preparation and labelling of Investigational Medicinal Product

Not applicable

6.8 Drug accountability

Not applicable

7. NON-INVESTIGATIONAL PRODUCT

Not applicable

7.1 Name and description of non-investigational product(s)

Not applicable

7.2 Summary of findings from non-clinical studies

Not applicable

7.3 Summary of findings from clinical studies

Not applicable

7.4 Summary of known and potential risks and benefits

Not applicable

7.5 Description and justification of route of administration and dosage

Not applicable

7.6 Dosages, dosage modifications and method of administration

Not applicable

7.7 Preparation and labelling of Non Investigational Medicinal Product

Not applicable

7.8 Drug accountability

Not applicable

8. METHODS

A list of data items obtained from the SEER 17 database is provided in Table 1.

Table 1. Retrieved SEER Research Plus Data Items

Data item name	Category name
Patient ID	Other
Age recode with single ages and 85+	Race and Age (case data only) or Age at Diagnosis
Sex	Race, Sex, Year Dx, Registry, County
Race recode (White, Black, Other)	Race, Sex, Year Dx, Registry, County
Origin recode NHIA (Hispanic, Non-Hisp)	Race and Age (case data only) or Race, Sex, Year Dx, Registry, County
Race and origin recode (NHW, NHB, NHAIAN, NHAPI, Hispanic)	Race and Age (case data only) or Race, Sex, Year Dx, Registry, County
Year of diagnosis	Race, Sex, Year Dx, Registry, County
Sequence number	Multiple Primary Fields
Record number recode	Multiple Primary Fields
Total number of in situ/malignant tumors for patient	Multiple Primary Fields
Total number of benign/borderline tumors for patient	Multiple Primary Fields
First malignant primary indicator	Multiple Primary Fields
Primary by international rules	Multiple Primary Fields
Diagnostic Confirmation	Site and Morphology
Site recode ICD-O-3/WHO 2008	Site and Morphology
Site recode ICD-O-3/WHO 2008 (for SIRs)	Site and Morphology
Primary Site - labeled	Site and Morphology
Laterality	Site and Morphology
ICD-O-3 Hist/behav	Site and Morphology
Grade (thru 2017)	Site and Morphology
Grade Clinical (2018+)	Site and Morphology
Grade Pathological (2018+)	Site and Morphology
Site recode - rare tumors	Site and Morphology
ICCC site recode extended 3rd edition/IARC 2017	Site and Morphology
AYA site recode 2020 Revision	Site and Morphology
Lymphoid neoplasm recode 2021 Revision	Site and Morphology
SEER Brain and CNS Recode	Site and Morphology
TNM 7/CS v0204+ Schema (thru 2017)	Site and Morphology
CS Schema - AJCC 6th Edition	Site and Morphology
Schema ID (2018+)	Site and Morphology
AJCC ID (2018+)	Site and Morphology
EOD Schema ID Recode (2010+)	Site and Morphology
Combined Summary Stage (2004+)	Stage - Summary/Historic
Summary stage 2000 (1998-2017)	Stage - Summary/Historic
Derived EOD 2018 Stage Group (2018+)	Stage - 8th edition
Derived SEER Cmb Stg Grp (2016-2017)	Stage - 7th edition
Derived AJCC Stage Group, 7th ed (2010-2015)	Stage - 7th edition
Derived AJCC Stage Group, 6th ed (2004-2015)	Stage - 6th edition
SEER modified AJCC stage 3rd (1988-2003)	Stage - Other
Lymphoma - Ann Arbor Stage (1983-2015)	Stage - Other
Tumor Size Summary (2016+)	Extent of Disease
CS tumor size (2004-2015)	Extent of Disease
EOD 10 - size (1988-2003)	Extent of Disease - Historic
Months from diagnosis to treatment	Therapy
RX Summ--Surg Prim Site (1998+)	Therapy
Reason no cancer-directed surgery	Therapy
Radiation recode	Therapy
Chemotherapy recode (yes, no/unk)	Therapy
B Symptoms Recode (2010+)	Site-Specific Data Items
CEA Pretreatment Interpretation Recode (2010+)	Site-Specific Data Items
Survival months	Cause of Death (COD) and Follow-up
Survival months flag	Cause of Death (COD) and Follow-up
Vital status recode (study cutoff used)	Cause of Death (COD) and Follow-up
COD to site recode	Cause of Death (COD) and Follow-up
SEER cause-specific death classification	Cause of Death (COD) and Follow-up
SEER other cause of death classification	Cause of Death (COD) and Follow-up

Patients are categorized into two age groups: children (aged 0-17 years at diagnosis) and young people aged 18-24 years at primary gastrointestinal cancer diagnosis. In principle, data is analyzed and presented by 1-year age category or by age group (<18 or 18-24 years at diagnosis), except for age distributions of specific patient populations (e.g. patients with colorectal carcinoma). When data from children and young people aged 18-24 years are analyzed together, then this is clearly stated in the accompanying text. Race is categorized into White, Black, and Other. Origin is categorized into Hispanic and non-Hispanic. Together, race and origin are reported in

Legend Table 2. Abbreviation: NOS, not otherwise specified. Symbols: * Contrary to the Rare Cancer Classification, cancers with ICD-O-3 morphology codes 8000-8009 ("neoplasms, NOS") and ICD-O-3 topography codes C015-C026 ("digestive organs") are not classified (e.g. morphology code 8002 as NEN; morphology codes 8000-8001 and 8003-8005 as epithelial tumors). Instead, these cancers are grouped within "rare other and unknown subtypes" in our study. This decision is made because – in our study population – the likelihood that digestive cancers of unspecified histologic subtype are of neuroendocrine or epithelial origin is not necessarily highest. In our young patient population, malignancies in these anatomic locations are relatively often other cancers, such as lymphomas, sarcomas or blastomas.

Seven common gastrointestinal cancers are specifically distinguished: Burkitt lymphoma (BL), undifferentiated embryonal sarcoma of the liver (UESL), neuroendocrine neoplasms (NEN), hepatoblastoma (HB), hepatocellular carcinoma (HCC), gastric carcinoma (GC), and colorectal carcinoma (CRC). These cancers are depicted in **blue** in Table 2. Subgroup analyses of patients with these malignancies are performed, with a special focus on patients with CRC.

For some of these common cancers, different histologic subtypes are distinguished (Table 3). Grading is based on ICD-O-3 and categorized as 1) Well differentiated, Grade I; 2) Moderately differentiated, Grade II; 3) Poorly differentiated, Grade III; 4) Undifferentiated or anaplastic, Grade IV. Stage at diagnosis is categorized into localized, regional, or distant according to the SEER Summary Staging system (<https://training.seer.cancer.gov/staging/systems/summary/>) by using the Combined Summary Stage variable (available for cases diagnosed between 2004-2019) or the Summary Stage 2000 variable (available for cases diagnosed between 2000-2003). In addition, the Ann Arbor classification is available for staging BL (for cases diagnosed between 2000-2015), and American Joint Committee on Cancer (AJCC) staging schemes are available for NEN, HCC, GC and CRC (Table 3). In any publications of analyses involving staging data, it is clearly stated that different staging schemes were used to stage cancers diagnosed in different years (e.g. AJCC 3rd edition for CRC diagnosed in 2000, and AJCC 8th edition for CRC diagnosed in 2019) – thereby acknowledging the limitations associated with these analyses.

Regarding the first course of treatment, surgery of the primary site, radiation and chemotherapy are dichotomously captured as "yes" or "no/unknown". Similarly, total hepatectomy with liver transplant is specified as "yes" or "no/unknown" for patients with primary hepatic malignancies – including UESL, HB, and HCC (Table 3). In any publications of analyses involving treatment data, the limitations of these data items are acknowledged, as outlined on the SEER website (<https://seer.cancer.gov/data-software/documentation/seerstat/nov2021/treatment-limitations-nov2021.html>).

Table 3. Categorization of data items analyzed for common cancer subtypes

Subtype	Primary site classification subgroups	Additional staging scheme subgroups	Grading scheme subgroups	Histologic classification subgroups	Surgery primary site (RX Summ--Surg Prim Site (1998+) variable)	Total hepatectomy with transplant (RX Summ--Surg Prim Site (1998+) variable)	Radiation (Radiation recode variable)	Chemotherapy (Chemotherapy recode (yes, no/unk) variable)
BL	ICD-O-3 C015-C026	Ann Arbor stage I-IV	NR	NR	Yes (values 10-90); No or unknown (values 0 and 99)	NR	Yes (all subtypes); No or unknown (incl. "refused" and "recommended, unknown if administered")	Yes; No or unknown
UESL	NR	N/A	NR	NR	Yes (values 10-90); No or unknown (values 0 and 99)	Yes (values 61 and 75); No or unknown (other values)	Yes (all subtypes); No or unknown (incl. "refused" and "recommended, unknown if administered")	Yes; No or unknown
NEN	ICD-O-3 C015-C017, C018.1 (appendix), C018 excl. C018.1, C019-C026	AJCC stage I-IV	ICD-O-3 Grade I-III	Rare Cancer Classification Cat. 1: 230-231 (well differentiated) vs. Cat. 2: 232-233 (poorly differentiated & MiNEN)	Yes (values 10-90); No or unknown (values 0 and 99)	NR	Yes (all subtypes); No or unknown (incl. "refused" and "recommended, unknown if administered")	Yes; No or unknown
HB	NR	N/A	ICD-O-3 Grade I-IV	NR	Yes (values 10-90); No or unknown (values 0 and 99)	Yes (values 61 and 75); No or unknown (other values)	Yes (all subtypes); No or unknown (incl. "refused" and "recommended, unknown if administered")	Yes; No or unknown
HCC	NR	AJCC stage I-IV	ICD-O-3 Grade I-IV	Rare Cancer Classification Cat. 1: 52 (HCC, NOS) vs. Cat. 2: 53 (HCC, fibrolamellar)	Yes (values 10-90); No or unknown (values 0 and 99)	Yes (values 61 and 75); No or unknown (other values)	Yes (all subtypes); No or unknown (incl. "refused" and "recommended, unknown if administered")	Yes; No or unknown
GC	ICD-O-3 C016.0-C016.9	AJCC stage I-IV	ICD-O-3 Grade I-IV	ICD-O-3 Cat. 1: 8140 (AC, NOS), Cat. 2: 8210 + 8220 + 8221 + 8261 + 8263 (AC in polyp/adenoma), Cat. 3: 8480-8482 (MAC), Cat. 4: 8490 (SRCC), Cat. 5: remaining cases (others/unknown) ¹⁶	Yes (values 10-90); No or unknown (values 0 and 99)	NR	Yes (all subtypes); No or unknown (incl. "refused" and "recommended, unknown if administered")	Yes; No or unknown
CRC	ICD-O-3 C018.0-C018.9, C019.9, C020.9	AJCC stage I-IV	ICD-O-3 Grade I-IV	ICD-O-3 Cat. 1: 8140 (AC, NOS), Cat. 2: 8210 + 8220 + 8221 + 8261 + 8263 (AC in polyp/adenoma), Cat. 3: 8480-8482 (MAC), Cat. 4: 8490 (SRCC), Cat. 5: remaining cases (others/unknown) ¹⁶	Yes (values 10-90); No or unknown (values 0 and 99)	NR	Yes (all subtypes); No or unknown (incl. "refused" and "recommended, unknown if administered")	Yes; No or unknown

New abbreviations: NR, not relevant; N/A, not available; Cat, category; AC, adenocarcinoma; MAC, mucinous adenocarcinoma; SRCC, signet ring cell carcinoma.

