10.2 Secondary study parameter(s)

Data will be presented quantitatively (numerically); stratified by age group (<18; 18-24 years at diagnosis).

Age-adjusted incidence and mortality rates are calculated as the average annual number of cases or deaths per million person-years at risk, respectively. For mortality rates, calendar year and age (<18; 18-24 years) represent year and age at death, respectively. Incidence rates of the common gastrointestinal malignancies are based on SEER 17 incidence data (2000-2019); mortality rates of malignant neoplasms of the digestive organs (ICD-O-3 topography codes C015-C026) are based on mortality data of the total U.S. population (1969-2019). In addition, incidence-based mortality (IBM) rates – for cases registered in SEER 17 – may be calculated to partition mortality by digestive cancer subtype (BL, UESL, NEN, HCC, HB, GC, and CRC)³³. The annual population size is obtained from the Census Bureau. Rates are age-standardized using the age structure of the 2000 U.S. standard population. Rates are calculated using SEER*Stat software and plotted using 3-year moving averages³⁴. When 3-year moving averages vary greatly, rates may be plotted using 5- or 7-year moving averages. Trends over time in incidence and mortality are analyzed by Poisson regression, with the calendar year as a continuous regressor variable. In addition, trends over time may be evaluated by linear regression modelling – a method frequently used in prior studies^{34,35} – to allow easier comparisons between studies, as well as with Jointpoint regression modelling to identify change points in the trends. Results are reported as average annual percent changes (AAPC) along with 95% confidence intervals and *P* values.

Trends over time in stage at diagnosis or first course treatments of patients with common GI malignancies are tested with logistic regression, with year of diagnosis as a continuous variable³⁴. The proportions of each stage at diagnosis or treatment category are plotted as weighted 3-year moving averages in percentages. When weighted 3-year moving averages vary greatly, results may be plotted using weighted 5- or 7-year moving averages.

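### Identifiable unknowns for surgery, transplant and radiation are pooled with 'no', so treated shares are lower bounds and time trends can pick up changes in record completeness

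*Combined protocol and SAP*

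**What the plan says.** Section 8 reduces each first-course treatment to two levels: "surgery of the primary site, radiation and chemotherapy are dichotomously captured as 'yes' or 'no/unknown". Table 3 gives the rules:

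- **Surgery, all seven common cancers:** "Yes (values 10-90); No or unknown (values 0 and 99"). Read in order, 0 is no surgery and 99 is unknown.
- **Transplant (UESL, HB, HCC):** "Yes (values 61 and 75); No or unknown (other values"). Code 99 is one of those other values.
- **Radiation:** "No or unknown (incl. 'refused' and 'recommended, unknown if administered").
- **Chemotherapy:** the source item in Table 1 is "Chemotherapy recode (yes, no/unk"), so by its name it arrives already pooled.

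Table 1 also retrieves "Reason no cancer-directed surgery", to which Table 3 gives no role.

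Section 8 adds a caveat: "In any publications of analyses involving treatment data, the limitations of these data items are acknowledged, as outlined on the SEER website".

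The two-level variables are used twice. Section 10.1 reports frequencies and proportions of treatment by age group. Section 10.2 states: "Trends over time in stage at diagnosis or first course treatments of patients with common GI malignancies are tested with logistic regression". The regressor in that model is the diagnosis year, kept continuous.

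**The concern.** First-course treatment is part of the main endpoint, and its time trend is a secondary endpoint. In a proportion, the no-or-unknown group fills the rest of the denominator. In the logistic model it is the zero outcome. Whatever its label, a patient with unknown surgery status counts in both places exactly like a patient who had none.

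Two consequences follow. The share reported as treated is the smallest value compatible with the data. And if completeness of the treatment record changed over the 20 diagnosis years, the fitted trend would mix that change with any real change in treatment.

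For surgery and the named radiation value, the merge is the plan's own choice, because the values are distinct in fields already retrieved. The plan treats stage differently: Table 4 keeps unknown or unstaged cases as a separate row. It provides no count of unknown treatment by year, no bounds and no sensitivity analysis.

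**Working it through.** The plan states no treated share, unknown share or sample size, so it offers no figure to reproduce. What follows is an illustration.

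**Inputs from the documents:** the Table 3 coding; diagnosis years 2000-2019, which is 20 years and 19 yearly steps (section 4.1); logistic regression on year (10.2); significance at P < 0.05 (10.2), taken as two-sided.

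**Assumed inputs:** the true treated share p, the unknown share u and the number of cases n.

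**Level.** If unknown status is unrelated to treatment:

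- pooled share = p(1 − u)
- shortfall = p × u
- bounds = p(1 − u) to p(1 − u) + u

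With p = 0.90:

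- u = 5%: pooled 0.90 × 0.95 = 85.5%; bounds 85.5% to 90.5%
- u = 1%: pooled 0.90 × 0.99 = 89.1%; bounds 89.1% to 90.1%

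**Trend.** Hold p at 0.90 and let u fall linearly from 5% to 1%:

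- odds at the start: 0.855/0.145 = 5.897
- odds at the end: 0.891/0.109 = 8.174
- ratio over 19 steps: 8.174/5.897 = 1.386
- per year: 1.386^(1/19) = 1.017

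A logistic fit to all 20 years also gives 1.017 per year, although true treatment never changed.

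**Range over other assumptions:**

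| True share p | Unknown share u, first to last year | Spurious OR per year |
|---|---|---|
| 0.90 | 10% to 2% | 1.030 |
| 0.80 | 10% to 2% | 1.018 |
| 0.80 | 5% to 0% | 1.012 |
| 0.80 | 2% to 0% | 1.005 |
| 0.90 or 0.80 | constant at 5% | 1.000 |

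**Chance of a false trend at 0.05.** For p = 0.90 and u falling from 5% to 1%, simulation gave 9%, 17% and 30% at n = 300, 1000 and 2000. For p = 0.80 and u falling from 2% to 0%, a normal approximation gives 5% to 7% for n from 200 to 1000. The excess over 5% is therefore small in small subgroups.

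**The opposite extreme.** Suppose every unknown was in fact untreated. With p = 0.90, the pooled share is correct and flat at 90%. Restricting to known status gives 0.90/0.95 = 94.7% in the first year and 0.90/0.99 = 90.9% in the last. The odds go from 18.0 to 10.0, a ratio of 0.556 over 19 steps, or about 0.97 per year. Here it is the known-only analysis that produces a false trend.

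**The case against.** The strongest reply is that the plan is open about the pooling. It never calls the category untreated, and it commits every publication using treatment data to acknowledging the limitations. One definition for all three treatments, matching what the chemotherapy field allows, is a defensible choice. This stands as far as labelling goes. It does not tell a reader whether the unknowns are few or many, or whether their share moved over time, and the retrieved data can show that for surgery.

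Four further limits also stand:

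- **Bias is not established.** A reader might infer that every treatment proportion is too low. The documents do not support that: a share is too low only if some unknowns were treated, and no unknown share is given. Nor do they show that completeness changed over time, which a false trend requires.
- **Dropping unknowns is not a cure.** A reader might infer that excluding them removes the bias. That holds only if unknown status is unrelated to treatment; the opposite extreme shows the harm when it is not.
- **Radiation is only partly separable.** Table 3 lists two values as included in its category. Nothing shows that the remaining no and unknown cases can be split.
- **The surgery-reason item is only a name.** Its values are not given, so the documents do not establish that it can confirm a true no.

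The cancers are rare, trends are run by cancer type and age group, and cases diagnosed at autopsy or by death certificate only are already excluded from treatment analyses. All of this may keep the practical effect small.

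**Conclusion.** The concern holds in a limited form. For surgery, transplant and one named radiation value, the plan merges identifiable unknowns with no, and that merged group acts as not treated in the proportions and trend models. The reported shares are lower bounds, and a trend could partly reflect record completeness.

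The size cannot be determined from the documents. Under the assumptions above it runs from no spurious trend (constant unknown share) to an odds ratio of 1.030 per year (p = 0.90, unknowns falling from 10% to 2%), with 1.017 for a fall from 5% to 1%. These figures assume a constant true share, a linear change in the unknown share, and unknown status unrelated to treatment. They show what could happen, not what did.

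The point does not extend to chemotherapy. It supports showing the unknowns and reporting both versions, not replacing the planned coding with a known-only analysis. It is a worthwhile, low-cost improvement.

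**What to change.** 1. In Table 3, hold surgery code 99 as a separate unknown category, also in the transplant item. Do the same for the radiation value that was recommended but not known to be given. Keep refused radiation as no.
2. Report unknown counts by diagnosis period and age group.
3. In 10.1 and 10.2, give surgery and transplant proportions, and any trends fitted to them, both with unknowns pooled as planned and among cases of known status, or as bounds. State that the known-only version assumes unknown status is unrelated to treatment.
4. For radiation, do this for the named value only, and note that other unknowns may remain within no.
5. Leave chemotherapy as yes versus no/unknown with the caveat already promised.

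The cost is a recode of retrieved fields, a few table rows, and a slightly smaller denominator in the known-only version.
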